Study Period IV: Only patients who do not participate in the CGAP study will move on to Study Period IV. During this 4-month phase, sites and patients will remain blinded to patients' treatment assignments. Patients will follow all study procedures during Study Period IV, but will

not receive galcanezumab or placebo. One month after Visit 12, if clinically warranted due to a worsening of symptoms, patients may start migraine prevention medications at the discretion of the investigator. The list of allowed preventive medications is provided in the concomitant medication study tool. At Visit 14 (Month 10), patients will return to the site for their last study visit and discharge from the study.

Patients who discontinue for any reason during Study Period IV will be expected to take the measurement for ET.

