8.2. Discontinuation from the Study

Some possible reasons that may lead to permanent discontinuation include:

- Enrollment in any other clinical trial involving an investigational product, or enrollment in any other type of medical research judged not to be scientifically or medically compatible with this study.
- Participation in the study needs to be stopped for medical, safety, regulatory, or other reasons consistent with applicable laws, regulations, and good clinical practice (GCP)
- Investigator Decision

- The investigator decides that the patient should be discontinued from the study.
- If the patient, for any reason, requires treatment with another therapeutic agent that has been demonstrated to be effective for the study indication (prevention of migraine) during Study Period III, discontinuation from the study occurs prior to introduction of the new agent.
- If, in the opinion of the investigator, a clinically significant event (CSE) occurs that warrants discontinuation of the study drug. A CSE will be defined as a moderate-to-severe AE, abnormal clinical sign, or clinical laboratory finding that may pose a serious risk to the well-being of the patient.
- Subject Decision
 - The patient requests to be withdrawn from the study.
- Sponsor Decision
 - If Lilly judges it necessary for medical, safety, regulatory, or other reasons, consistent with applicable laws, regulations, and good clinical practice.

Patients who discontinue the study early (Study Period III) will have end-of-study (ET) procedures performed as shown in the Schedule of Activities (Section 2) and are requested to proceed into the post-treatment phase.

Patients who discontinue the study early (Study Period IV) will have end-of-study (ET) procedures performed, as shown in the Schedule of Activities (Section 2).

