ePRO	electronic patient-reported outcomes
ERB	Ethical Review Board
ET	early termination
FEAE	follow-up emergent adverse event: an event that first occurred or worsened during the follow-up period (Study Period IV) when compared to the double-blind treatment period (Study Period III)
FSH	follicle-stimulating hormone
GCP	good clinical practice
GGT	gamma glutamyltransferase
GLIMMIX	generalized linear mixed model
HbA1c	glycated hemoglobin
HCRU	healthcare resource utilization
HDL	high-density lipoprotein
IB	Investigator’s Brochure
ICF	informed consent form
ICHD	International Classification of Headache Disorders

IHS	International Headache Society
investigational product	A pharmaceutical form of an active ingredient or placebo being tested or used as a reference in a clinical trial, including products already on the market when used or assembled (formulated or packaged) in a way different from the authorized form, or marketed products used for an unauthorized indication, or marketed products used to gain further information about the authorized form.
IB	Investigator's Brochure
ICH	International Conference on Harmonisation
IgM	immunoglobulin M
INR	International Normalized Ratio
IRB	institutional review board
ITT	intention to treat: The principle that asserts that the effect of a treatment policy can be best assessed by evaluating on the basis of the intention to treat a patient (that is, the planned treatment regimen) rather than the actual treatment given. It has the consequence that patients allocated to a treatment group should be followed up, assessed, and analyzed as members of that group irrespective of their compliance to the planned course of treatment.
IUD	intrauterine device
IUS	intrauterine system
IWRS	interactive web-response system
LOCF	last observation carried forward
MedDRA	Medical Dictionary for Regulatory Activities
MHD	migraine headache day
MIDAS	Migraine Disability Assessment test
MSQ v2.1	Migraine Specific Quality of Life Questionnaire version 2.1
MMRM	mixed models repeated measures
MMRM-CAT	categorical mixed models repeated measures
PD	pharmacodynamics
PGI-I	Patient Global Impression of Improvement
PGI-S	Patient Global Impression of Severity
PK	pharmacokinetics

PPS	Per-Protocol Set
PSMQ-M	Patient Satisfaction with Medication questionnaire-modified
Q4W	administration once every 4 weeks
QTc	corrected QT interval
QTcF	Fridericia's corrected QT interval
QTcLCTPB	Large Clinical Trial Population Based QT Correction
RBC	red blood cell

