To evaluate pharmacodynamics (target engagement) of LY2951742	Plasma concentrations of CGRP
To assess changes in efficacy outcomes during Study Period IV as collected by electronic patient-reported outcomes (ePRO) diary data	In Study Period IV: 
 
• Mean changes from baseline in migraine headache days (SP III and SP IV combined)
 
• Time to first loss of response (in SP IV) among patients who meet the 50% response rate criteria at the end of the double-blind treatment phase
 
• Time to initiation of treatment with a migraine prevention medication (in SP IV)
 

Abbreviations: CGRP = calcitonin gene-related peptide; MHD = migraine headache day.

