- **50% responders sustained for all six months during treatment phase in the number of migraine headache days** is defined as meeting the 50% responder criteria in the number of migraine headache days for Months 1-6 in the double-blind treatment phase. Anyone else are non-responders, including those who discontinued early and those who completed 6-month treatment phase but did not meet 50% response criteria for one or more of the 6 months.
- **Time to first 50% response (in months)** is defined as the first month when 50% response is met during the double-blind treatment phase (SP III). If a patient has not met a 50% response during SP III, they will be censored at the last month where the 50% response status is not missing.
- **Time to first loss of 50% response in the post-treatment phase (in months)** is calculated for Month 6 50% responders as the time from the end of treatment phase to the first month in Study Period IV at which these patients no longer meet the 50% response criteria. Patients who continue meeting the criteria until the end of the study will be censored.
- **Time to initiation of treatment with a migraine preventive medication (in days) in the post-treatment phase** is defined as the date of start of the migraine preventive medication (based on information collected from concomitant medication electronic case report form [eCRF]) in the post-treatment follow-up phase (SP IV) minus the last visit date of SP III. If a patient did not initiate preventive treatment during SP IV, they will be censored at the disposition date of SP IV. This analysis will be conducted only for patients who entered SP IV.
- **Number of migraine headache days with photophobia and phonophobia** is calculated as the total number of migraine headache days with an answer of "yes" to Question 7 in a 30-day period.

- **Number of migraine headache days with nausea and/or vomiting** is calculated as the total number of migraine headache days with an answer of “yes” to Question 8 in a 30-day period.
- **Number of migraine headache days with aura** is calculated as the total number of migraine headache days with an answer of “yes” to Question 12 in a 30-day period.
- **Number of migraine headache days with prodromal symptoms other than aura** is calculated as the total number of migraine headached days with an answer of “yes” to Question 13 in a 30-day period.

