### **5.5.9. Concomitant Therapy, Migraine Prevention Therapy, and Migraine Acute Treatment.**

The proportion of patients who received concomitant medication will be summarized for ITT population for Study Period III and for the post-treatment population for Study Period IV separately. The concomitant therapy does not include migraine acute (abortive) treatments or migraine prevention therapy.

Concomitant therapies for study period III are those which started, stopped or continued in study period III. If medication started and stopped on the same day of injection, it will still be considered as concomitant medication for SP III. If medication started before the first day of injection but stopped on the same day of injection, then it will not be counted as concomitant medication for SP III.

Concomitant therapies for study period IV are those which either started, stopped or continued in Study Period IV. If medication started and stopped on the first day of SP IV, it will still be considered as concomitant medication for SP IV.

Treatment group comparisons will be done using the Fisher's exact test for Study Period III with ITT population. Descriptive statistics only will be presented for the treatment groups in Study Period IV with the post-treatment population.

Similar outputs for migraine prevention therapy will be created for SP III and SP IV. As mentioned in the previous section, the definition of the prevention therapy will be reviewed by medical before DBL.

Similar outputs for migraine acute treatment will be created for SP III and SP IV separately. The categorization is based on Section 5.5.8.

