#### **Time to Event Measures**

For the following time to event measures, a Kaplan-Meier curve of the time to event and treatment group comparison using log-rank test stratified by baseline MHD frequency category (<8 vs ≥8 migraine headache days per 30-day period) will be provided.

- Time to first 50% response in double-blind treatment phase
- Time to first loss of 50% response in post-treatment phase (SP III completer only)
- Time to initiation of preventative treatment for migraine or probable migraine in post-treatment phase (SP III completer only)

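### Do the two post-treatment time-to-event endpoints lack a single population and a rule for patients who start a new preventive?

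*SAP*

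**What the plan says.** Two of the other secondary endpoints in SAP 4.2.2 follow patients after treatment stops.

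*Time to starting a migraine preventive.* SAP 5.4.1 measures it in days from the last Study Period III (SP III) visit, censors at the Study Period IV (SP IV) disposition date, and adds: "This analysis will be conducted only for patients who entered SP IV". SAP 5.5.10.3 lists it among the Kaplan-Meier and stratified log-rank analyses as "Time to initiation of preventative treatment for migraine or probable migraine in post-treatment phase (SP III completer only".

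*Time to first loss of 50% response.* SAP 5.4.1 takes patients who were 50% responders at Month 6 and counts the first SP IV month in which the diary no longer shows that response. On censoring it says: "Patients who continue meeting the criteria until the end of the study will be censored". SAP 5.5.10.3 limits this endpoint to SP III completers as well.

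Three further passages bear on these. Protocol 8.2 says that patients who stop early in SP III "are requested to proceed into the post-treatment phase". Protocol 5.1 has a rule that applies once a month has passed since Visit 12, and it reads: "if clinically warranted due to a worsening of symptoms, patients may start migraine prevention medications at the discretion of the investigator". SAP 5.5.9, after describing the concomitant-medication tables by period, says: "Similar outputs for migraine prevention therapy will be created for SP III and SP IV".

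**The concern.** On the first endpoint, having entered SP IV and having completed SP III are different conditions. Early discontinuers may enter SP IV, and completers who roll over to the extension study do not. Two programmers could therefore build two datasets. The choice would not be neutral: under Protocol 8.2 a patient who needs another effective preventive during SP III leaves before starting it. Such a patient could be among the SP IV entrants but not among the completers, and is plausibly more likely than most to have the event.

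On the second endpoint, the SAP says nothing about a responder who starts a permitted preventive. If that drug holds the diary count down, a later loss is delayed or never seen, and response kept up by another drug is read as persistence of the randomised treatment. The risk sets are small, so a few such patients could be visible in the curves.

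**Working it through.** **Planning numbers.** SAP 5.2 gives 451 randomised, 15% discontinuation and 383 completing. Protocol 7.8.1 gives about 240 rolling over to the extension, skipping SP IV. I read the 383 as SP III completers.

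- Completers: 451 × (1 − 0.15) = 383.35, which reproduces the stated 383.
- Completers not rolling over: 383 − 240 = 143.
- Discontinuers: 451 − 383 = 68.

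**Population.** The documents do not give the share of discontinuers who enter SP IV, so I vary it.

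| Discontinuers entering | SP IV entrants | Discontinuers' share |
|---|---|---|
| 0% | 143 | 0% |
| 25% (17) | 160 | 17/160 = 10.6% |
| 50% (34) | 177 | 34/177 = 19.2% |
| 100% (68) | 211 | 68/211 = 32.2% |

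The difference would matter if both populations were open. Set side by side, they are not:

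1. The sentence in SAP 5.4.1 is a limit. It removes anyone who did not enter SP IV; it does not promise to include everyone who did.
2. The parenthesis in SAP 5.5.10.3 is a second limit. It removes anyone who did not complete SP III.
3. Including discontinuers breaks the second limit. Including rolled-over completers breaks the first, and they have no SP IV disposition date at which to be censored.
4. The general rule in SAP 5.5.1.3, that SP IV analyses use the post-treatment population, holds only where nothing else is specified. SAP 5.5.10.3 specifies something else.

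What remains is completers who entered SP IV, the 143 in the first row. The larger rows describe a reading that SAP 5.5.10.3 rules out.

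**Loss of response.** The definition uses diary response alone, so each case has an outcome:

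- Falls below 50%, then starts a preventive: event at the first month below 50%. A later start cannot undo a first loss.
- Starts a preventive, later falls below 50%: event at that month, possibly delayed.
- Starts a preventive and stays at or above 50% to the end: censored as still responding.

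Only the last two groups are affected. SP IV is divided into Months 7 to 10, and preventives are allowed only from one month after Visit 12. For the last group, a Month 6 responder would have to hold response through about Month 7, worsen enough to warrant a preventive, and still meet the 50% criterion in every month to the end.

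**Size per patient.** Assume that rollover is unrelated to arm and response, and that Month 6 response is 40–60% on galcanezumab and 20–40% on placebo. The rates are assumptions; the documents give none. The non-rollover share is 143/383 = 0.373.

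- Each galcanezumab arm: 113 × 0.85 × 0.373 = about 36; × 0.40 to 0.60 = 14.3 to 21.5 responders.
- Placebo: 225 × 0.85 × 0.373 = about 71; × 0.20 to 0.40 = 14.3 to 28.6 responders.
- With no other censoring, turning one censored patient into an event moves the final estimate by 1/n: 1/21.5 to 1/14.3 = 4.6 to 7.0 points on galcanezumab, and 1/28.6 to 1/14.3 = 3.5 to 7.0 points on placebo.

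These figures are per patient. The documents give no basis for the number of such patients.

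**The case for a change.** The strongest argument for changing the text is timing. Under SAP 5.7 and 5.8.1, SP IV-only analyses wait for the final lock, by which time the project statistician, analysts and programmers have been unblinded since the interim lock. Anything left open could be settled by people who have seen SP III results by arm. That is a good reason to fix open choices early, but the texts leave little to settle. The population follows from applying both limits, and the loss-of-response outcome follows from its definition. One phrase used in both places would be tidier and would not change the analysis.

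A second argument is that starting a preventive ought to count as loss of response, since the interest is in what happens once galcanezumab stops. That is a legitimate estimand, but not plainly a better one. It would label patients who still meet the 50% criterion as having lost response, on an event at the investigator's discretion. It would also overlap with the separate endpoint that already times preventive starts. Leaving the start out of the definition agrees with the protocol's intention-to-treat definition, which keeps patients in their group "irrespective of their compliance to the planned course of treatment".

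A related suggestion is to rerun the combined-period models, such as "Mean changes from baseline in migraine headache days (SP III and SP IV combined", without the months after a preventive start. Nothing has been shown to be wrong with those models. The rerun would also have to treat the removed months as missing at random in patients selected because they were worsening.

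What stands is that the SAP does not discuss this intercurrent event, so the loss-of-response curves should be read alongside the preventive-initiation curve and the SP IV preventive-use tables.

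**Conclusion.** No change follows. The population point is a gap in wording that an analyst fills correctly by obeying both sentences: SP III completers who entered SP IV, about 143 at planning numbers if 383 complete SP III and about 240 roll over. The loss-of-response point is a fair trade-off. The SAP uses diary response whatever else the patient takes, and reports preventive starts separately. The affected group is narrow and may be empty; each patient censored as still responding would carry roughly 3.5 to 7.0 points of an arm's final Kaplan-Meier estimate under the assumed response rates, with no other censoring and rollover unrelated to arm and response. The direction of any difference between arms cannot be determined. Both are other secondary endpoints outside the multiplicity adjustment, which SAP 5.5.10.3 confines to the primary analysis, so the primary result, type I error and power are unaffected.

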#### **Distribution of Response Rates**

Overall x% response rate during the double-blind treatment phase will be estimated for X=0, 5, 10, ..., 95, and 100, using GLIMMIX model as described earlier in this section. These estimated response rates will be plotted and points within each treatment arm will be connected to show a

curve of response rates. No statistical comparisons will be conducted among different treatment arms.

#### Analysis for PGI-S

Change from baseline in PGI-S scores will be analyzed.

PGI-S responder analysis will be conducted.

#### Analysis for PGI-I

The PGI-I raw value will be analyzed with a mixed model repeated measures analysis with PGI-S baseline score.

PGI-I responder analysis (Weighted Mean of PGI-I Responder analysis) will be analyzed. 95% confidence interval will be generated using nonparametric Monte Carlo bootstrap.

**Table CGAN. 5.5 Primary, Secondary and Exploratory Efficacy Variables and Analysis Methods**

Efficacy Variables	Analysis in SP III	Analysis in SP III/IV	Analysis in SP IV only
Number of MHD	MMRM/ANCOVA	MMRM	NA
Number of MHD with Criteria C	MMRM	NA	NA
Number of migraine headache hours	MMRM	NA	NA
Number of migraine attacks	MMRM	NA	NA
Number of days with acute medication use	MMRM	NA	NA
Number of MHD with acute medication use	MMRM	MMRM	NA
Proportion of MHD with acute medication use	MMRM	NA	NA
Number of headache days	MMRM	NA	NA
Number of moderate-severe headache days	MMRM	NA	NA
Number of headache hours	MMRM	NA	NA
Number of ICHD MHD	MMRM	NA	NA
Mean severity of migraine headache	MMRM	NA	NA
Number of MHD with nausea and/or vomiting	MMRM	NA	NA
Number of MHD with photophobia and	MMRM	NA	NA

phonophobia			
Number of MHD with aura	MMRM	NA	NA
Number of MHD prodrome symptoms other than aura	MMRM	NA	NA
Number of non-MHD with aura	MMRM	NA	NA
Proportion of Aura within migraine attack	MMRM	NA	NA
Number of classes of acute medication use	MMRM	NA	NA
Number of classes of acute medications used on MHD	MMRM	NA	NA
Average number of classes of acute medication use	MMRM	NA	NA
Average number of classes of acute medication use on MHD	MMRM	NA	NA
Number of MHD with menstrual period	MMRM	NA	NA
Number of days with triptans use	MMRM	NA	NA
Number of MHD with triptans use	MMRM	NA	NA
Number of days with NSAIDS/Aspirin use	MMRM	NA	NA
Number of MHD with NSAIDS/Aspirin use	MMRM	NA	NA
Number of days with Acetaminophen/paracetamol use	MMRM	NA	NA
Number of MHD with Acetaminophen/paracetamol use	MMRM	NA	NA
Number of days with Ergots use	MMRM	NA	NA
Number of MHD with Ergots use	MMRM	NA	NA
Number of days with Anti-nausea use	MMRM	NA	NA
Number of MHD with Anti-nausea use	MMRM	NA	NA
Number of days with Multi-Class acute medication use	MMRM	NA	NA
Number of MHD with Multi-Class acute medication use	MMRM	NA	NA
Number of days with acute medication use on non-headache days	MMRM	NA	NA
PGI-S	MMRM	MMRM	NA

PGI-I (adjusting for PGI-S)	MMRM	NA	NA
MSQ Total	MMRM	MMRM	NA
MSQ Role Function-Restrictive domain	MMRM	MMRM	NA
MSQ Role Function-Preventive domain	MMRM	MMRM	NA
MSQ Emotional Function domain	MMRM	MMRM	NA
MIDAS Total (sum of item 1, 2, 3, 4, and 5)	MMRM	MMRM	NA
MIDAS individual items (item 1, 2, 3, 4, 5, A, and B)	MMRM	NA	NA
HCRU Summary	Descriptive	NA	Descriptive
HCRU Migraine related events/100-patients-year	Descriptive	NA	Descriptive
HCRU Employment status	Descriptive	NA	Descriptive
Number of weekly MHD in month 1	GLIMMIX	NA	NA
X% response rate (X=50, 75, or 100)	GLIMMIX	GLIMMIX	NA
30% response rate	GLIMMIX	NA	NA
Distribution of response rate in SP III	GLIMMIX	NA	NA
Time to first 50% response in SP III	KM/log-rank test	NA	NA
Maintenance of 50% response for the last 3 months or 6 months	Logistic regression	NA	NA
Time from the end of SP III to no longer meeting 50% response criterion	NA	NA	KM/log-rank test
Time from the end of SP III to start use of preventative treatment for migraine	NA	NA	KM/log-rank test
PGI-S responder (2 $\geq$ improvement)	GLIMMIX	NA	NA
PGI-I responder (Top 2 categories)	Weighted mean	NA	NA
MIDAS 50% responder at month 6	GLIMMIX	NA	NA
MSQ Role Function-Restrictive responder ( $\geq$ 25)	Logistic regression	NA	NA
PSMQ-M summary (with positive response)	Logistic regression	NA	NA

Abbreviations: ANCOVA = analysis of covariance; GLIMMIX = Generalized linear mixed model (for binary variables); HCRU = HealthCare Resource Utilization; ICHD = International Classification of Headache Disorders; KM/log-rank test = Kaplan Meier curve and stratified log-rank test; MHD=migraine headache days; MIDAS = Migraine Disability Assessment; MMRM = Mixed models repeated measures; MSQ = Migraine-Specific Quality; NA = not applicable. PGI-I = Patient Global Impression-Improvement; PGI-S = Patient Global Impression-Severity; PSMQ-M = Patient Satisfaction with Medication Questionnaire-Modified; SP = Study Period;

### **5.5.11. Quality-of-Life (QoL) Analyses**

#### **5.5.11.1. MSQ**

The mean change from baseline to each post-baseline visit for Study Period III and Study Period III/IV for MSQ total score and 3 domain scores will be evaluated using MMRM as described in Section 5.5.10.1. The endpoint for comparing LY2951742 with placebo will be estimated using a CONSTRAST statement in PROC MIXED as the average across Months 4-6 and overall (Month 1- Month 6).

MSQ Role Function-Restrictive domain responders (based on the average score of change from baseline at month 4, 5, and 6  $\geq 25$ ) in SP III will be analyzed using logistic regression.

